## **2.2.4 Safety variables**

### **2.2.4.1 Secondary safety variables**

#### **2.2.4.1.1 Adverse events**

Presence (Y/N) of

- Adverse Event (AE)
- Serious AE
- Non-serious AE
- Death
- AE leading to permanent withdrawal of study medication
- Severe AE
- Drug-related AE
- AE of special interest
  - Serious infections including opportunistic infections
  - Malignancies including lymphoma
  - Serious cardiovascular events
  - Congestive heart failure
  - Demyelinating-like disorders
  - Aplastic anemia, pancytopenia, thrombocytopenia, neutropenia and leucopenia
  - Serious bleeding events
  - Lupus and lupus-like illness
  - Serious skin reactions (eg, Stevens Johnson Syndrome, toxic epidermal necrosis, and erythema multiforme)

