**Table 11–1: Assignment of Adverse Events to Study Periods**

Type of Subject	Assignment Rule Based on AE Start Date	Assignment
Subjects who enter the open-label period	
1. Start date is on or after first study drug administration during the double-blind period and on or before the last study drug administration in the double-blind period + 70 days and before the start date and time of OL-CZP or OL-OT.
 
Note: If a subject continues in the study with OL-OT visits but without taking any relevant other medication, there will be no start date of the other treatment period and all AEs with a start date within 70 days after last administration will be assigned to the DB period.
	Double-blind TEAE
	
2. Start date is on or after the start date of OL-CZP and on or before the last study drug administration in the OL-CZP period + 70 days and
 
 
• before the start date of OL-OT (for subjects moving into OL-OT), or
 
• before the SFE period start (for subjects moving into SFE period)
 
	Open-label CZP TEAE
	
3. Start date is on or after the start date of OL-OT.
 
Note: Other treatment adverse events will not be summarized, but only presented in listings
	Open-label other treatment TEAE
Subjects who enter the pre-SFE period	Start date is after the last double-blind or OL-CZP dose + 70 days and is before the SFE period start.	Pre-SFE AE
Subjects who enter the open-label SFE period	Start date is on or after the SFE period start and on or before the SFE period end + 70 days.	SFE TEAE

If AE intensity or relationship is missing, then the given event will be imputed as severe or related, respectively.

The frequency of all AEs including TEAEs will be presented for each treatment group separately by System Organ Class, high level term, and preferred term. The data will be displayed as number of subjects experiencing the AEs, percentage of subjects, and number of AEs. Certain summaries will also include exposure-adjusted incidence rates and event rates. TEAEs will be summarized by treatment and period as described in [Section 3.6](#).

The following AE summaries will be presented:

- Overview of TEAE
- Overview of Pre-SFE AEs

- TEAE
- Serious TEAE
- Non-serious TEAE
- TEAE with fatal outcome
- TEAE leading to permanent withdrawal of study medication
- Severe TEAE (included in TEAE table by intensity)
- Drug-related TEAE (included in TEAE table by relationship)

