5. Demyelinating-like disorders will be presented in table which is based on the SMQ = “Demyelination”. The SMQ search should include all TEAEs which code to a PT included in Scope=Narrow group within the SMQ. TEAEs which code to a PT included in the Scope=Broad group within the SMQ should be excluded from the search.
6. Aplastic anemia, pancytopenia, thrombocytopenia, neutropenia, and leucopenia. These will be presented in a table using the criteria SMQ = “Haematopoietic cytopenias” in the subset of Serious TEAEs.
7. Serious bleeding events. These will be presented in a table using the criteria SMQ = “Haemorrhage terms (excl laboratory terms)” in the subset of Serious TEAEs.
8. Lupus and lupus-like illness. These will be manually identified by the study physician from the TEAE table. No separate table is planned.
9. Serious skin reactions (eg, Stevens-Johnson Syndrome, toxic epidermal necrosis, and erythema multiforme). These will be manually identified by the study physician from Serious TEAE table. No separate table is planned.

The tables for 1, 2, 3, 5, and 6 above, will include the exposure-adjusted incidence rate (EAIR) with associated 95% CI, and the exposure-adjusted event rate (EAER) as described below.

Although not officially AEs of interest, the following events will also be summarized as described in the AEs of Interest – Cimzia Program 2018-01-05 guidance document.

1. Hepatic events. These will consist of a subset of all TEAEs, identified using the following 5 SMQs: Cholestasis and jaundice of hepatic origin; Hepatic failure, fibrosis, and cirrhosis and other liver damage-related conditions; Hepatitis, noninfectious; Liver-related investigations, signs and symptoms; and Liver-related coagulation and bleeding disturbances.
2. Hypersensitivity reactions and anaphylactic reactions. Hypersensitivity reactions will be summarized as any TEAEs occurring on the same day or the day after injection was received, which code to the following preferred terms: Administration site hypersensitivity, Documented hypersensitivity to administered product, Drug hypersensitivity, Hypersensitivity, Hypersensitivity vasculitis, Infusion site hypersensitivity, Injection site hypersensitivity, Medical device site, hypersensitivity, Type II hypersensitivity or Type IV hypersensitivity reaction. Anaphylactic reactions will be defined using an algorithmic approach as described in the “AEs of Interest – Cimzia Program 2018-01-05” guidance document.

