The summary of TEAEs, serious TEAEs, and TEAEs leading to permanent withdrawal of study medication will include the EAIR (with corresponding 95% exact CI) and EAER. The confidence interval for the EAIR will be based on Poisson rate CIs. The bounds of the exact 95% CIs are estimated by

$$\text{lower bound} = \frac{1}{2 \cdot t} \cdot \chi^2_{2 \cdot (\text{number of patients with events}), 0.025} \quad \text{and} \quad \text{upper bound} = \frac{1}{2 \cdot t} \cdot \chi^2_{2 \cdot (\text{number of patients with events} + 1), 0.975}$$

$\chi^2_{n,\gamma}$  denotes the chi-distribution with n degrees of freedom and quantile  $\gamma$  and t is the exposure censored at the time of occurrence of the AE.

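### The cytopenia AE of special interest is defined without a seriousness limit, but its dedicated table and rates count serious events only

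*SAP*

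**What the plan says.** SAP Section 2.2.4.1.1 defines the secondary safety variables as presence (yes/no) of an event and lists nine AEs of special interest. Some entries carry a seriousness limit in their name, for example "Serious bleeding events" and "Serious infections including opportunistic infections". The cytopenia entry does not; it reads "Aplastic anemia, pancytopenia, thrombocytopenia, neutropenia and leucopenia".

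Section 11.2 sets out how each entry is summarized. Item 6 repeats the unrestricted cytopenia name, then says the table will be produced "using the criteria SMQ = “Haematopoietic cytopenias” in the subset of Serious TEAEs". Section 11.2 adds: "The tables for 1, 2, 3, 5, and 6 above, will include the exposure-adjusted incidence rate (EAIR) with associated 95% CI", together with the EAER. Item 6 is therefore one of the tables that carry rates. The SAP gives no reason for the filter. It calls its account of these events brief and refers to a program guidance document for more.

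**The concern.** The definition and the analysis rule describe different variables. Under Section 2.2.4.1.1 a subject with an investigator-reported, non-serious neutropenia, leucopenia or thrombocytopenia is a *yes*. Under Section 11.2, item 6, the same subject is not counted. The item 6 table is the one place where the plan groups these terms and attaches exposure-adjusted rates, so it is the natural place to look for this risk. Its unrestricted heading does not warn that non-serious events have been removed. A short or empty table could then be taken to mean few cytopenias of any kind, when it shows only that few were serious.

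**Working it through.** The SAP states no figure that needs reproducing. The check sets the two sections side by side and follows one subject through the planned outputs.

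**Step 1: does item 6 follow the pattern of the other entries?**

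| Item | *Serious* in the name (2.2.4.1.1) | Source of events (11.2) | Agree? |
|---|---|---|---|
| 1 Infections | yes | Serious TEAE table, plus a separate opportunistic-infection table | yes |
| 2 Malignancies | no | two SMQ tables, no seriousness filter | yes |
| 3 Cardiovascular events | yes | serious TEAEs | yes |
| 4 Congestive heart failure | no | TEAE table, manual review | yes |
| 5 Demyelinating-like disorders | no | all TEAEs, narrow scope | yes |
| 6 Cytopenias | no | serious TEAEs only | **no** |
| 7 Bleeding events | yes | serious TEAEs | yes |
| 8 Lupus | no | TEAE table, manual review | yes |
| 9 Skin reactions | yes | Serious TEAE table, manual review | yes |

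Eight of the nine entries agree. For item 5 the SAP is explicit: "The SMQ search should include all TEAEs which code to a PT included in Scope=Narrow group within the SMQ". Hepatic events, which the SAP says are not officially AEs of interest, are also drawn from all TEAEs. The presence or absence of *Serious* therefore carries meaning throughout the list, except at item 6.

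**Step 2: where does a subject with one non-serious neutropenia TEAE appear?**

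- Item 6 table: not counted.
- Item 6 EAIR and EAER: not in either numerator. Section 11.2 censors EAIR exposure only at the event being analyzed, so this subject also contributes uncensored exposure.
- General TEAE tables: counted. Section 11.2 says "The frequency of all AEs including TEAEs will be presented for each treatment group separately by System Organ Class", and also by high level term and preferred term.
- Rates for the general table: counted. "The summary of TEAEs, serious TEAEs, and TEAEs leading to permanent withdrawal of study medication will include the EAIR" and the EAER.
- Non-serious TEAE tables: counted.
- Laboratory outputs (Section 11.3): a low count enters the low/normal/high shift tables and the minimum-value summaries. It enters the marked-abnormality table only if extreme enough, for example neutrophils below 1000/µL.

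**Step 3: does any other output group the terms?** None applies this SMQ to all TEAEs. Two of the general outputs also work preferred term by preferred term with a cut-off: the table of TEAEs at 1% or more on CZP and above placebo, and the relative-risk plot for terms above 1% on CZP. With the 150 subjects per group planned in Section 2.4, one subject is 1/150 = 0.7% and two are 2/150 = 1.3%, so a term needs two CZP subjects to reach either. As an illustration only, four subjects with four different cytopenia terms would each be at 0.7% and would miss both outputs, while the grouped figure would be 4/150 = 2.7%. All four would still be listed in the full TEAE table.

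**Step 4: how large is the undercount?** If *s* is the share of subjects with any cytopenia TEAE who have a serious one, the item 6 table omits a fraction 1 − *s*. The SAP gives neither *s* nor an expected incidence, so this cannot be evaluated.

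**The case against.** The strongest reply is that nothing is lost. Non-serious cytopenias are tabulated by arm under their preferred terms, with rates, and a term with two or more CZP subjects can reach the relative-risk plot. Low counts below grade 3 are shown in the shift and minimum-value tables whether or not an AE was reported. Heart failure and lupus have no dedicated table at all, so the SAP accepts the general tables as a route for an AE of interest. The serious-only search may also be a program standard explained in the guidance document, which is not at hand.

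Much of this stands, and it rules out stronger readings. A reader might infer that non-serious cytopenias go untabulated, that an imbalance in them would be invisible, or that the laboratory tables show only grade 3 and above. Sections 11.2 and 11.3 contradict all three. A reader might also want to put a percentage on the undercount, but any serious share or incidence would be an assumption without a source in the SAP.

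The mismatch itself survives. Laboratory values are not reported events, and Section 11.3 attaches no exposure-adjusted rates to them. Heart failure and lupus are to be identified from the whole TEAE table, so their non-serious cases remain in scope. A guidance document might justify the filter, but it would not make Section 2.2.4.1.1 or the item 6 heading describe what the table contains.

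**Conclusion.** The point holds as an inconsistency in current SAP text with a limited consequence. The dedicated cytopenia table, its EAIR and its EAER undercount the variable that Section 2.2.4.1.1 defines, by an amount the document does not allow one to calculate. No grouped count or exposure-adjusted rate of all cytopenia TEAEs is planned elsewhere. This rests on reading Section 2.2.4.1.1 literally, which the other eight entries support. The SAP alone does not settle whether the filter or the definition is the slip. Severity is minor to moderate: the output is descriptive, the underlying events remain visible, and no efficacy conclusion changes.

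**What to change.** In Section 11.2, item 6, apply the SMQ Haematopoietic cytopenias to all TEAEs, with EAIR (95% CI) and EAER, and show the serious subset as a second block of the same table. The second block keeps comparability with outputs already produced at the Week 52 lock. Section 4.3 has the adverse event tables produced again at the final lock, so the change can be made there.

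If the program guidance does intend serious events only, say so in Section 2.2.4.1.1 and in the item 6 heading, with the reason. Readers would then know to look for non-serious cytopenias in the general TEAE and laboratory tables.

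The first option costs one amended sentence, one removed filter and a longer table. The second costs wording only, but leaves the grouped count of all cytopenias unreported.

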### Date imputation for incomplete or missing start and/or stop dates

Where an AE start date is (partially) missing, the AE will be considered TE if possible.

Imputation rules provided in [Section 4.2.4](#) are based on the assumption that if the start date is incomplete, either day only is missing, or day and months are missing, or date is completely missing.

Although the algorithms for treatment-emergence depend on the onset date, imputation rules are provided for resolution date as well, as these may be needed for certain statistical analyses, such as an analyses of AE prevalence or AE duration.

In order to identify differences between CZP and placebo with respect to TEAEs, the relative risk (CZP/placebo) of the most common TEAEs (incidence >1% for the PT in the CZP treatment group) will be presented graphically by descending relative risk including the 95% CI.

Listings for TEAEs, serious TEAEs, TEAEs leading to withdrawal of study medication, and TEAEs with fatal outcome will be provided. A glossary for the reported terms will also be generated utilizing SOC, HLT, and PT.

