## **2.4 Determination of sample size**

Subjects will be randomized in a 1:1 ratio to the CZP 200mg Q2W and placebo treatment groups. The expected response rates for ASDAS-MI at Week 52 are 40% and 20% for CZP and placebo, respectively. A total sample size of 300 (150 subjects per treatment group) provides 95% power to detect a statistically significant difference in the ASDAS-MI response rate at Week 52 between CZP and placebo based on a 2-sided significance level of 0.05.

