### 8.1.3.2 Multiple imputation

Investigators will be given discretion to discontinue study treatment for subjects not responding in order to provide them with other treatments for the condition. Therefore, in many cases, missing efficacy data due to study treatment discontinuation should be dependent on the observed efficacy scores, but independent of unobserved data. This would be consistent with a missing at random (MAR) pattern of missingness. In order to investigate the efficacy results under the assumption of data being MAR, a multiple imputation method will be applied as follows:

1. The continuous ASDAS score at each visit will be calculated using the methods described in [Section 8.1.1](#) (including the application of LOCF if only one component is missing). Visits with more than one component missing will be set to missing. ASDAS data collected after the discontinuation of double-blind study treatment will be treated as missing in the original data set for this sensitivity analysis. Hence, all open-label period data is excluded from this analysis.
2. For subjects with a non-monotone (intermittent) missing pattern, MCMC will be used to impute their missing intermittent ASDAS scores including treatment arm, region, MRI/CRP

classification and ASDAS measurement from previous visit(s) as explanatory variables in the model. This will be done 100 times limiting the imputation to in range results.

After this step there will be 100 datasets containing all subjects however the only missing data will be a monotone missing data pattern. A variable called “\_imputation\_” will identify each of the 100 imputed datasets output.

3. The remaining missing data for all subjects with a monotone missing data pattern will be imputed using regression with treatment arm, region, MRI/CRP classification and ASDAS measurement from previous visit(s) as explanatory variables. This model will be run once for each of the imputed datasets limiting imputation to in range results.
4. The ASDAS change from Baseline to Week 52 will be calculated using the complete datasets (with no missing data) and categorized as: ASDAS-MI or not ASDAS-MI (as defined in [Section 8.1.1](#))

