- Serious TEAE by relationship
- Non-serious TEAE by relationship
- Fatal TEAE by relationship
- TEAE of special interest (see below)
- TEAE sorted by incidence of PTs in the CZP 200mg group (SOC and higher level term [HLT] will not be utilized)
- Non-serious TEAE with an incidence of more than 5% in 1 of the 2 randomized groups (HLT will not be utilized)
- Non-serious TEAE with an incidence of more than 5% in 1 of the 2 randomized groups by relationship (HLT will not be utilized)
- TEAE subject numbers
- TEAEs with a CZP incidence  $\geq 1\%$  and CZP incidence  $>$  PBO incidence

The AEs of interest and the approach for summarizing them is briefly described below. Further information is provided in the guidance document (AEs of Interest – Cimzia Program 2018-01-05).

1. Serious infections, including opportunistic infections. Serious infections will be summarized using the Serious TEAE table. No separate table is planned. In addition, opportunistic infections (including tuberculosis) will be presented in a table using UCB-defined search criteria.
2. Malignancies, including lymphoma. These will be presented in 2 tables using the Standardized MedDRA Query (SMQ) criteria “Malignant or unspecified tumours” and “Malignant tumours” respectively.
3. Serious cardiovascular events (also called major adverse cardiac events or MACE). These will be presented in a table including all serious TEAEs with the SMQs of “Haemorrhagic central nervous system vascular conditions”, “Conditions associated with central nervous system haemorrhages and cerebrovascular accidents”, and “Ischaemic central nervous system vascular conditions” with the exception of events coding to a PT of “Transient ischaemic attack”, including all serious TEAEs with the HLT of “Ischaemic coronary artery disorders” except events coding to PTs of “Chest Pain” or “Chest discomfort” and including all serious

TEAEs with HLTs of “Heart Failures NEC”, “Left Ventricular Failures”, or “Right Ventricular Failures” and which also code to the SOC of “Cardiac Disorders”.

4. Congestive heart failure. These will be manually identified by the study physician from the TEAE table. No separate table is planned.

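### The CZP/placebo relative-risk figure and the list of TEAEs more frequent on CZP use unadjusted subject incidence, which would run against CZP if placebo subjects switch to open-label treatment earlier

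*SAP*

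**What the plan says.** Section 11.2, under the subheading on date imputation, plans a display whose stated purpose is to find differences between the arms: "the relative risk (CZP/placebo) of the most common TEAEs (incidence >1% for the PT in the CZP treatment group"), which "will be presented graphically by descending relative risk including the 95% CI". No exposure adjustment is mentioned. The same section fixes how TEAEs are tabulated: "The data will be displayed as number of subjects experiencing the AEs, percentage of subjects, and number of AEs". Its list of summaries also includes TEAEs with CZP incidence of at least 1% and "CZP incidence $>$ PBO incidence".

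Table 11–1 sets the counting window. A double-blind TEAE must start within 70 days of the last double-blind dose. For subjects entering the open-label period it must also start "before the start date and time of OL-CZP or OL-OT". For subjects going straight into the SFE it must start before the SFE period does.

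On who leaves double-blind treatment, Section 8.1.3.2 says: "Investigators will be given discretion to discontinue study treatment for subjects not responding in order to provide them with other treatments for the condition". Section 2.4 says: "The expected response rates for ASDAS-MI at Week 52 are 40% and 20% for CZP and placebo, respectively".

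Exposure-adjusted rates do appear elsewhere in Section 11.2. The tables of TEAEs, serious TEAEs and TEAEs leading to withdrawal carry the EAIR with an exact 95% CI and the EAER, as do several tables of events of interest.

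**The concern.** A ratio of subject proportions compares like with like only if both arms are watched for about the same time. Here the watching time depends on when a subject leaves double-blind treatment, and the SAP's own expectations point to earlier exit on placebo. A shorter placebo window lowers the placebo proportion of every preferred term at once. The ranked figure would then shift upward as a whole. A term with equal rates in the two arms could also enter the list of terms more frequent on CZP only because CZP subjects were observed longer. No interval is described for that list.

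A second, smaller point concerns selection. The figure chooses terms on CZP incidence alone, so a term at or below 1% on CZP is left out however common it is on placebo.

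**Working it through.** **The plan's own figures.** The SAP gives no figure for this display and no switching rate by arm. Its only related design figures are the response rates. With 150 per arm and 40% versus 20%, the pooled normal approximation gives z = (0.20 − 1.96 × 0.0529)/0.0516 = 1.86, or about 97% power. That agrees with the stated 95%, so the response rates are taken as given. They imply expected non-response of 60% on CZP and 80% on placebo. "Subjects will be randomized in a 1:1 ratio to the CZP 200mg Q2W and placebo treatment groups", so unequal allocation plays no part.

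**Model.** Both arms have the same constant hazard h per year. A fraction d leaves double-blind treatment at week s. TEAEs are then counted for a further a weeks (0 if other treatment starts at once, up to 10 if none starts). Everyone else is counted to week E. E is 52 if the SFE starts then, and up to 60 otherwise (Week 50 dose + 70 days).

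Incidence = 1 − [(1 − d)·exp(−hE/52) + d·exp(−h(s + a)/52)]

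The relative risk is CZP incidence divided by placebo incidence.

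**Assumed inputs (not in the SAP).** d = 40/15%, 50/25% or 60/30% (placebo/CZP); s = 20 or 28; h = 0.05 or 0.20.

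**One case in full.** d = 60/30%, s = 20, h = 0.05, a = 0, E = 52:
- placebo: 1 − (0.4 × 0.9512 + 0.6 × 0.9810) = 0.0309
- CZP: 1 − (0.7 × 0.9512 + 0.3 × 0.9810) = 0.0399
- relative risk = 1.29, although the hazards are identical

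**All twelve combinations:**

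| Tail a for leavers | Stayers counted to E | Relative risk under equal hazards |
|---|---|---|
| 0 weeks | 52 | 1.13 to 1.29 |
| 5 weeks | 52 | 1.10 to 1.22 |
| 10 weeks | 52 | 1.07 to 1.17 |
| 0 weeks | 60 | 1.16 to 1.33 |
| 10 weeks | 60 | 1.10 to 1.21 |

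In the first row, mean observed time is 32.8 to 42.4 weeks on placebo and 42.4 to 48.4 on CZP.

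**Sensitivity to the exit pattern** (h = 0.05, no tail, E = 60; the low end has exit spread evenly over Weeks 12–52, the high end has all exit at Week 16). Exit of 20/20% gives 1.00, 30/15% gives 1.08 to 1.14, and 60/20% gives 1.26 to 1.52 (1.25 for the low end before rare-event rounding).

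**Would the SAP's existing exposure remove the shift?** Mostly, but not entirely. Take 60/20% exit spread over Weeks 12–52 (mean 32), a rare event, and a last dose 2 weeks before the switch.
- Counting window: placebo 0.4 × 60 + 0.6 × 32 = 43.2 weeks; CZP 0.8 × 60 + 0.2 × 32 = 54.4 weeks. The unadjusted ratio is 54.4/43.2 = 1.26.
- Section 11.1 method 3 adds 70 days with no cut at open-label start, so leavers contribute 40 weeks: placebo 48, CZP 56. The rate ratio is (54.4/56)/(43.2/48) = 1.08.
- The 14-day rule (methods 2 and 4) gives placebo 0.4 × 52 + 0.6 × 32 = 40 and CZP 0.8 × 52 + 0.2 × 32 = 48. The rate ratio is (54.4/48)/(43.2/40) = 1.05.
- Person-time matched to the counting window gives 1.00.

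**Selection.** With 150 per arm, incidence above 1% means at least 2 CZP subjects. A term in 1 CZP subject (0.67%) and 10 placebo subjects (6.7%) is omitted.

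**Precision.** With equal incidence p and 150 per arm, the 95% CI of one relative risk extends by a factor exp(1.96·√(2(1 − p)/(150p))) each way: 4.9 at 2%, 2.7 at 5%, 2.0 at 10%.

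**The case against.** The strongest reply is that earlier placebo exit is an inference. A reader might take the SAP to say that placebo subjects leave sooner. It does not. It gives no rate or timing by arm, and missing ASDAS-MI at Week 52 is not its rule for leaving double-blind treatment. If the drug had no effect at all, response would give no reason for unequal exit and the ratio would be 1.00. This stands, so the point must be conditional.

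A reader might also infer that terms seen mainly on placebo can never appear in the figure. That is wrong: a term at 2% on CZP and 10% on placebo is plotted, with a relative risk of 0.2. Only terms at or below 1% on CZP are lost. The list is one-sided by its own definition and is one of many summaries.

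Nor does the SAP ignore exposure. A reader of the main TEAE table will have exposure-adjusted rates by arm for each preferred term.

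Finally, the figure is descriptive, with no test or decision attached. A shift of 1.1 to 1.3 is small beside the interval for a single term, so it would rarely change how one term is read. What remains is that the shift, if present, acts on all terms in the same direction, and these two displays are the ones that set the arms directly against each other.

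**Conclusion.** The point holds conditionally. If placebo subjects leave double-blind treatment earlier, which is the direction the SAP's own expectations suggest, the figure and the list would overstate CZP risk across all preferred terms. The size is about 1.07 to 1.3 under assumed discontinuation of 40/15% to 60/30%, constant equal hazards, exit around Week 20 or 28, and a tail of 0 to 10 weeks. It would be larger with earlier or more unequal exit and nil with equal exit. No primary or secondary efficacy conclusion is affected, and the EAIR and EAER tables contain most of the harm. This is a cheap improvement to two safety displays.

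**What to change.** Plot the EAIR ratio (CZP/placebo) by preferred term with a Poisson-based 95% CI, or add it beside the relative risk. End person-time where the double-blind TEAE window ends: last double-blind dose + 70 days, cut at the start of OL-CZP, OL-OT or the SFE, and censored at the first event. Show the EAIR comparison in the list of terms more frequent on CZP. Select terms for the figure on incidence above 1% in either arm.

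The cost is modest but is more than a wording change. Section 11.1 method 4 already derives event-censored exposure for each preferred term, but none of the methods states the cut at open-label start, so exposure needs a small re-derivation. The SAP schedules the double-blind outputs for the Week 52 lock (Section 4.3) and describes them as already produced (Section 2.2.1.3), so the result would be a supplementary output labelled as added after unblinding.

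### The CZP/placebo relative-risk figure selects adverse event terms on CZP incidence alone, which tilts the display upward for terms near the 1% cut-off and omits placebo-excess terms seen in 0 or 1 CZP subjects

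*SAP*

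**What the plan says.** The figure is described in SAP Section 11.2, near the end of the sub-section on imputing incomplete dates. Its purpose carries no direction: "In order to identify differences between CZP and placebo with respect to TEAEs". The same sentence defines the display: "the relative risk (CZP/placebo) of the most common TEAEs (incidence >1% for the PT in the CZP treatment group) will be presented graphically". The entry condition has no placebo-arm or pooled part. The selected terms "will be presented graphically by descending relative risk including the 95% CI".

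Three other outputs in Section 11.2 bear on the point:

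- All adverse events are tabulated for each treatment group by system organ class, high level term and preferred term.
- One listed summary uses a cut-off that treats the arms alike: "Non-serious TEAE with an incidence of more than 5% in 1 of the 2 randomized groups (HLT will not be utilized").
- Another listed summary is restricted to terms with CZP incidence of at least 1% that also exceeds placebo incidence. A display aimed at CZP excess therefore already exists.

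**The concern.** The variable that decides entry is the numerator of the plotted ratio. Among infrequent terms with equal true rates, those that happened to come out high on CZP get in. Those that came out low do not, and the placebo count has no say. Two things follow for a figure meant to show differences in either direction. Point estimates for terms just above the cut-off lean upward, and the descending sort puts the largest of them first. Terms with a placebo excess and 0 or 1 CZP subjects never appear, while their mirror images meet the entry rule. What is at stake is how the figure reads, not any test or endpoint.

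**Working it through.** **Arm size.** The SAP gives no number for this figure, so the arm size comes from Section 2.4: "A total sample size of 300 (150 subjects per treatment group) provides 95% power". As a check on that input, take its 40% and 20% response rates at 2-sided 0.05. The null standard error is √(2 × 0.30 × 0.70/150) = 0.0529, and the alternative one is √((0.24 + 0.16)/150) = 0.0516. Power is Φ((0.20 − 1.96 × 0.0529)/0.0516) = 96.9%. A continuity correction gives 95.9% and Fisher's exact test 96.0%. The stated 95% is consistent with 150 per arm and is not in dispute.

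**Entry rule.** More than 1% of 150 means at least 2 CZP subjects. The same count applies to any arm of 100 to 199.

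**Terms with no true difference.** Let X (CZP) and Y (placebo) be independent Binomial(150, p), conditioned on X ≥ 2. The SAP states no preferred-term rates, so p is an assumption, shown over a range. At p = 1%:

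- P(X = 0) = 0.99^150 = 0.221 and P(X = 1) = 150 × 0.01 × 0.99^149 = 0.336, so P(X ≥ 2) = 0.443.
- E[X | X ≥ 2] = (1.5 − 0.336)/0.443 = 2.63, while E[Y] stays at 1.5. The ratio of expected counts is 1.75.

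That ratio is not an average of plotted values, because it includes terms with no placebo events. The table therefore gives the geometric mean of (X + 0.5)/(Y + 0.5) over selected terms, by exact enumeration.

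| True rate, both arms | Geometric mean RR | CZP above placebo | CZP below placebo | No placebo events |
|---|---|---|---|---|
| 0.5% | 2.76 | 86% | 3% | 47% |
| 1% | 1.89 | 69% | 13% | 22% |
| 2% | 1.27 | 51% | 31% | 5% |
| 3% | 1.08 | 46% | 40% | 1% |
| 5% | 1.007 | 45% | 44% | 0% |

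The tilt does not come only from empty placebo cells. All of those fall in the CZP-above column. Removing them at 1% leaves 69 − 22 = 47% above against 13% below. At 2% it leaves 51 − 5 = 46% against 31%.

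**Terms with a true placebo excess.** P(omitted) = P(X ≤ 1) = (1 − p)^150 + 150p(1 − p)^149, with p the CZP rate.

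| True CZP vs placebo | Omitted | Mirror-image CZP excess omitted |
|---|---|---|
| 0.5% vs 2% | 83% | 20% |
| 1% vs 3% | 56% | 6% |
| 2% vs 5% | 20% | 0.4% |

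As observed counts, 1 vs 8 (Fisher p = 0.036) and 0 vs 6 (p = 0.030) are not plotted. Their mirror images 8 vs 1 and 6 vs 0 qualify, although 6 vs 0 has no computable ratio.

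**Confidence intervals.** With Wald intervals on the log relative risk, the share of selected no-difference terms whose 95% interval lies wholly above 1 is 0.00% at a true rate of 0.5%, 0.01% at 1%, 0.24% at 2%, 0.7% at 3% and 1.5% at 5%. All are below the nominal 2.5%.

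**The case against.** The figure is a descriptive display of the most common events, with no test or decision rule, and a focus on the active drug is a legitimate choice that this SAP makes elsewhere. Each ratio carries its interval: an inflated term such as 2 vs 1 has relative risk 2.0 with interval 0.18 to 21.8, which few would read as harm. Nothing is lost from the report, since all events are tabulated by arm. The 1 vs 8 example is 8/150 = 5.3% on placebo, so if non-serious it also enters the 5% table.

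All of this stands, and it rules out several stronger readings that a reader might infer:

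- That the figure generates false harm signals. The interval results above show that it does not.
- That relative risks are inflated across the figure. The effect is gone by about 5% true incidence.
- That reductions on CZP cannot be shown for infrequent terms. A term at 2 vs 7 is plotted, with relative risk 2/7 = 0.29.
- That placebo-excess events go unreported. They are missing from one figure only.

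What the objection does not answer is the mismatch between purpose and rule. The stated aim is to identify differences without direction, and the CZP-excess view already has its own table. A complete table elsewhere does not make a one-sided figure two-sided.

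**Conclusion.** The point holds as a minor one. The entry rule gives a one-sided display for a two-way purpose. Upward bias in the point estimates is material for true incidences up to about 2 to 3%. The range matters because the SAP's own 1% cut-off puts the start of the figure there. Omission concerns only terms with 0 or 1 CZP subjects. The sizes rest on about 150 subjects per arm, independent binomial counts and assumed preferred-term rates. The direction follows from the rule itself. No endpoint, test or safety tabulation depends on it.

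**What to change.** In Section 11.2, change the entry condition to incidence above 1% for the preferred term in either randomized treatment group in the double-blind period. This follows the pattern already used at 5% for non-serious events. Alternatively, require more than 1% pooled over both arms, which is at least 4 of 300. The rest of the figure can stay as planned.

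Under either rule the geometric mean relative risk of selected no-difference terms is 1.00 at every rate checked, with equal shares above and below 1. At a true rate of 1% the shares are 44% each under the either-group rule and 38% each under the pooled rule. Under the either-group rule, omission of placebo-excess terms falls from 83% to 16% (0.5% vs 2%), from 56% to 3% (1% vs 3%) and from 20% to 0.1% (2% vs 5%).

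The cost is one phrase in the SAP and one selection line in the program. The either-group rule also plots more terms: a no-difference term at 1% true incidence enters with probability 69% instead of 44%. The pooled rule gives 35% for the same term, so it avoids lengthening the figure with rare terms.
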